### **The impact of attrition.**

It is anticipated that some attrition will occur in this population. Based on our current pilot study and previous marijuana studies, we anticipate a 10% attrition rate between Appointment 1 baseline session and Appointment 2 the experimental session, though we have not experienced and do not anticipate differential attrition by condition. Thus, to allow for attrition, we assume a 90% retention rate over the course of data collection. To adjust for this attrition rate, we will recruit  $n\approx 111$  participants ( $n=37$  per group). Our approach to power analysis and accounting for attrition is extremely conservative, in that the techniques we will utilize in data analysis use state of the art recommendations in iterating the estimation of missing data (Schafer & Graham, 2002; Little, 1988). All analyses are intent-to-treat and all available data are utilized in analyses.

### **Analysis Plan for Hypotheses 1 and 2**

Analyses will be conducted primarily on the SAS system for Windows Version 9.1, which includes capabilities to test multilevel models that include nonlinear effects and missing data (Cohen et al., 2013). Preliminary analyses will include checking the data for normality and reliability. To test the success of random assignment, the equivalence of conditions across all pretest measures will be assessed via t-tests on continuous items (e.g., depressive symptoms) and  $\chi^2$  tests of categorical items (e.g., race). We will use the Bonferroni approach (Keppel, 1991) to correct for alpha inflation with a familywise alpha of .05. Tests of the main hypotheses for effects of THC on primary outcomes will be conducted in a multilevel framework to account for the repeated observations within participants over time. Random coefficient regression (RCR; Cohen et al., 2013) models in SAS Proc Mixed will be utilized for continuous outcomes (e.g., working memory, drug reward).

### **Effects of THC Potency on THC Blood Levels, Working Memory, and Reward**

The first aim is designed to test whether the “potency” of marijuana in terms of THC level in the plant translates directly to THC levels in the blood. To test **Hypothesis 1**, those individuals who receive the high THC strain will demonstrate significantly greater blood THC levels, we will utilize random coefficient regression (RCR; Cohen et al., 2013) via SAS Proc Mixed. The between subjects factor will be strain (high THC versus medium THC versus low THC) and the within subjects factor is time (Time 1, Time 2, Time 3, Time 4). Blood level of THC is the dependent measure. The test of the strain X time interaction will indicate whether the pattern of effects is such that blood levels increase to a greater degree and remain higher across the course of the study in the strains with higher THC. Thus, we expect both a significant interaction as well as a main effect of strain. Assuming a significant omnibus test of the interaction, we will decompose the interaction

via planned posthoc contrasts in order to understand at which time points the three strains are different. At Appointment 1, Time 1 (baseline) we do not expect differences in THC since none of the participants will have switched strains. Appointment 2, Time 2 is the sober, before use at Time 3. Thereafter, we expect a difference in THC at Appointment 2, Time 3 in the high THC versus the medium and low THC groups, and that while all groups will decrease in THC over the course of the laboratory appointment between Time 3 and 4, the high THC group will continue to show higher blood levels than the medium THC group, and the medium THC group will show higher blood levels than the low THC group. Note that we will include a quadratic effect in the multilevel model both to appropriately model the quadratic effect and whether that quadratic trend differs by condition. It is important to note that since we are not directly controlling administration, and have instructed participants to ingest the marijuana ad libitum, that they themselves may moderate their consumption to achieve “desired” THC levels, as our pilot data suggest. Thus, those in the low and medium THC group may ingest more in order to match their typically desired level, and thus the groups might converge. In this case, it is possible that we may see fewer difference in blood levels of THC, or non-significant differences at some timepoints across groups.

**Hypothesis 2** tests whether blood levels of THC are positively associated with diminished working memory and greater rewarding effects of the marijuana, operationalized with the DEQ. If analyses of Hypothesis 1 show that there are main effects by group suggesting that the higher THC strain results in significantly higher THC levels in the blood than the medium or low THC strains, the between-groups variable for models testing Hypothesis 2 will be group and we will include all four time points. Since participants were randomly assigned to group, this test allows for the highest internal validity in terms of causal conclusions about the effects of THC. If, on the other hand, participants titrate their own use such that there are few reliable between-groups differences, then actual blood levels of THC will become the between-groups (continuous) independent variable in tests of Hypothesis 2 and we will utilize timepoints 3-4 as the within-subjects effect of time. Our preliminary studies confirm wide variability in THC levels even among individuals using the same strain, so there will be adequate between-participant variability for these analyses. In either case, we will again use the RCR approach described above, and standard approaches to the estimation of interactions in regression (Aiken & West, 1991) in the case of a continuous IV (i.e., mean-centering prior to creation of the interaction term). In each model, the predictors will include the group variable (or continuous THC blood levels), a time variable, and their interaction.

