### **Power Analysis and Sample Size Requirement for Hypotheses 1 and 2**

Sample size was selected to permit analysis of the primary research questions at two-tailed alpha of .05 and power level of .80. Estimates of effect size follow Cohen (1988) and were conducted in G\*Power 3 (Faul et al., 2007). The primary analysis is the test of the strain X time interaction effects across repeated assessments of THC in the blood as well as assessments of working memory and the rewarding effects of the marijuana. To be conservative, we thus estimated an ICC of .60. Using a mixed model ANOVA design, with three groups, four assessment points, and an average ICC = .6 between assessment points, a total n=99 (33 per group) will allow us to detect an interaction effect as small as  $f=.12$ .

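### The strain main effect on blood THC averages in the pre-assignment Time 1 value and does not adjust for it, which weakens the test that helps choose the Hypothesis 2 model

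*Protocol*

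**What the plan says.** All references are to section IV of the protocol.

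- **Model.** Under Effects of THC Potency on THC Blood Levels, Working Memory, and Reward, blood THC is the dependent measure, strain is the between-subjects factor, and "the within subjects factor is time (Time 1, Time 2, Time 3, Time 4"). A strain x time interaction and a strain main effect are both expected, and a quadratic time effect is included.
- **Timing of Time 1.** Marijuana Administration at Home places the purchase instruction at the end of Appointment 1, after the baseline measures. Of Time 1 the protocol itself says "we do not expect differences in THC since none of the participants will have switched strains".
- **Use of the main effect.** If Hypothesis 1 shows main effects by group, "the between-groups variable for models testing Hypothesis 2 will be group and we will include all four time points". If participants titrate and few group differences appear, observed blood THC replaces group as the predictor. The protocol credits the group version with the better internal validity. The predictors listed for Hypothesis 2 are group (or blood level), time and their interaction.
- **Baseline adjustment.** None is given for Time 1 blood THC. In section XII, covarying baseline is mentioned only for the depression and anxiety inventories, and only if needed.
- **Power.** "The primary analysis is the test of the strain X time interaction effects across repeated assessments of THC in the blood", and the sample size is set "at two-tailed alpha of .05 and power level of .80" with "an average ICC = .6 between assessment points", 99 participants analysed and f=.12.

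**The concern.** Time 1 is a pre-randomisation measurement for participants who are assigned a strain. The arms then share one expected value there, and any observed difference is chance. Giving each strain its own free Time 1 level has two consequences.

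1. The strain main effect becomes an average over four occasions, at least one of which carries no effect. The estimate shrinks towards zero, and between-person variation that Time 1 could explain stays in the error term.
2. The interaction test in effect compares raw changes from Time 1. Each arm's chance baseline deviation is subtracted in full, not in proportion to its correlation with later values.

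The first consequence matters more, because group main effects feed the decision on how Hypothesis 2 is analysed. A real potency effect that fails this test could be taken as titration. Hypothesis 2 would then move from the randomised comparison to an observational one.

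**Working it through.** **Inputs from the power section:** N=99 (33 per group), 3 groups, 4 occasions, rho=.60, f=.12, alpha .05.

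**Assumptions (not in the protocol):** equal variances (set to 1) and equal correlations; time as a four-level factor; strain effect linear across arms (-d, 0, +d), zero at Times 1 and 2 and equal at Times 3 and 4. This profile is closest to the stated expectation. All 99 are treated as randomised.

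**1. The plan's own figure.** lambda = f² x N x m/(1-rho) = .0144 x 99 x 4/.4 = 14.256. On F(6, 288) the power is .811, so the stated .80 reproduces.

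**2. Scale of the effect.** The covariance of Times 2-4 minus Time 1 is (1-rho)(I+J). For the pattern (0,1,1) the quadratic form is [2 - 4/4]/.4 = 2.5. Setting 33 x 2 x d² x 2.5 = 14.256 gives d² = .0864.

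**3. Strain main effect for this same d.**

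| Definition | Mean effect | Variance | lambda | Power |
|---|---|---|---|---|
| Times 1-4 (as written) | d/2 | (1+3rho)/4 = .700 | 66 x .0216/.700 = 2.04 | .223 |
| Times 2-4, unadjusted | 2d/3 | (1+2rho)/3 = .733 | 66 x .0384/.733 = 3.46 | .355 |
| Times 2-4, adjusted for Time 1 | 2d/3 | (1-rho)(1/3+rho) = .373 | 66 x .0384/.373 = 6.79 | .626 |

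Dropping Time 1 from the average gives the first step and adjustment the second. The estimand also changes, from 0.50 to 0.67 of the acute difference.

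**4. Strain x time.** The covariance of Times 2-4 given Time 1 is (1-rho)(I+rho J). The quadratic form is [2 - .6 x 4/2.8]/.4 = 1.143/.4, so lambda = 14.256 x 1.143 = 16.29 and power is .868, a gain of 5.7 points.

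**5. Sensitivity of the interaction gain** (effect rescaled each time so that the planned test keeps lambda = 14.256).

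- *Profile, at rho .6:* Time 4 effect 75% of Time 3, 5.5 points; 50%, 4.8; Time 3 only, 2.1. With 25% or 50% of the later effect already present at Time 2, 8.3 or 10.8. A full difference at the sober Time 2, which the protocol does not expect, gives 12.8.
- *Correlation, base profile:* rho .3, 11.7; .45, 8.5; .75, 3.3; .9, 1.2.
- *SD at Times 3-4 relative to Times 1-2, rho .6:* ratio 1.5, 0.7; ratio 2, 5.7; ratio 3, 12.3.
- *Unequal correlations averaging .6* (.7 between Times 1-2, .9 between Times 3-4, .5 otherwise) *with SD ratio 2:* about 0.5.

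**6. Sensitivity of the main-effect gain** (as written, then Times 2-4 adjusted). At rho .6: .189 to .535 with the Time 4 effect at 50%; .103 to .244 with Time 3 only; .334 to .833 with 25% at Time 2. Base profile: .138 to .558 at rho .75 and .079 to .502 at rho .9. It is a gain in every case.

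**7. Simulation** (4,000 replicates, base profile): interaction 81.1% against 86.3%; main effect 22.1% against 62.6%. Type I error was 4.4% to 5.5% for all four tests.

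**The case against.** The strongest reply is that nothing planned is invalid. A factorial with baseline as a repeated level is a standard choice. The primary interaction test is unbiased, holds its type I error, and has the power claimed for it. **That stands in full.** A reader might infer that the trial is underpowered for its primary question or that its primary test is biased; the protocol's own inputs support neither. A reader might also take a fixed loss of about 6 points from the interaction result. That does not stand either: the figure depends on an effect profile and variances that the protocol does not give, and it can be near zero or about double.

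Other points on that side:

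- *The main effect is not the primary test.* True, but it is an expected result of Hypothesis 1 and it bears on the Hypothesis 2 model, so its weakness has consequences.
- *The .22 to .63 contrast bundles two changes and two estimands.* True; the .35 in between separates them.
- *Planned contrasts compare strains at each time point, so an acute difference could still be seen.* True. The decision rule is also loosely worded, speaking both of main effects and of few reliable group differences. Misrouting of Hypothesis 2 is therefore a risk, not a certainty.
- *The protocol includes a quadratic trend.* If time enters as linear plus quadratic, the interaction has 4 df and the free Time 1 level becomes a fitted starting level. The structural point remains, but the figures above are for the four-level form only.
- *The number randomised is unclear.* Edible users form naturally occurring groups in the design overview, so treating all 99 as randomised follows the power section and may overstate the randomised sample.
- *An analysis plan not shown could add a covariate.* It could, but the protocol already fixes the outcome occasions and factors.

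**Conclusion.** The point holds as a matter of efficiency. As written, the strain main effect includes an occasion that cannot show an effect and leaves baseline variation unadjusted. Under the assumptions listed, its power is about .22, against .63 for a baseline-adjusted average over Times 2-4. The exact values depend on those assumptions, but the direction was the same in every scenario checked. The size of the gain on the primary strain x time test is uncertain: about 6 points in the base case, and from under 1 to about 12 across other plausible profiles, variances and correlations. The reason to change is the role of the main effect in choosing between the randomised and the observational version of Hypothesis 2. No bias or type I error is being corrected.

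**What to change.** Keep the same SAS Proc Mixed model and all the data, and change the wording as follows.

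- For the randomised flower strains, constrain Time 1 to one common mean, with strain terms at Times 2-4 only. Alternatively, remove Time 1 from the outcomes and enter it as a covariate with its interaction with time.
- Test strain at Times 2-4. Define the main effect of strain as the baseline-adjusted average over Times 2-4, and name that effect as the criterion for choosing the Hypothesis 2 model.
- Treat working memory in the group branch of Hypothesis 2 the same way; the cognitive battery is given at all four sessions.
- For the self-selected edible groups use the covariate form, since randomisation does not justify a common Time 1 mean there.

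The cost is protocol text and model code: no new visits, samples or participants. The covariate form loses anyone without a Time 1 sample; the constrained form keeps them.

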### **Overview and Design of Study 1 (e.g., Aim 1, Hypotheses 1 and 2).**

Study 1 is designed to test the hypothesis that a high THC strain of marijuana will be associated with greater blood levels of THC and greater harmful effects, as compared to a lower THC strain, when used in a

naturalistic environment. To that end, regular flower marijuana users, who, according to our preliminary data, typically use marijuana with a THC potency of ~18%, will be assigned to use one of three strains with no CBD but with different THC potencies (low, medium, or high: e.g. 6%, 12%, or 18% THC for smoked flower) and regular edible marijuana users who typically purchase 10 mg products will be allowed to use as they normally would (producing naturally occurring low, medium, and high groups: e.g. less than 2.5mg to greater than 10 mg THC n=33 per group) for five days prior to participating in the experimental session. Measures will be collected at Appointment 1: (Baseline/**Session 1**), after 5 days of using the assigned strain, but in a sober condition before use in our mobile laboratory at Appointment 2: (**Session 2**), they will then return to their home to use the assigned strain and return to the mobile laboratory (**Session 3**), and 60 minutes after their last use at home (**Session 4**). Details regarding sample ascertainment, marijuana administration, timing of measures to be collected, power analyses, and the analytic plan for Study 1 follow. Thus, Study 1 will involve a 3 Cannabis strains: high, medium, and low THC x 4 (Time: 1, 2, 3, 4) mixed factorial design.

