After consulting with CU legal counsel, we now plan to utilize a mobile lab, which will facilitate blood and data collection on site, rather than transporting the subjects to the lab for assessments as we did in our preliminary study. The mobile lab will be based on the Dodge/Mercedes Sprinter van platform (see pictures) with comfortable seating and space for blood draws and cognitive testing on laptops. This change addresses potential problems, like the variable (10 - 20 minute) delay between the time the individual uses the marijuana and the time we can collect the first blood sample, self-report, and cognitive data. This change also addresses concerns with how feasible it is to recruit a sufficient number of subjects within a short driving radius of the lab. There are other advantages; the mobile lab will be outfitted in a comfortable, lounge-like atmosphere with appropriate décor (i.e., glassware and artwork found in dispensaries). This is consistent with the reviewer’s suggestion to create a more naturalistic environment for the assessments. Thus, rather than bring the subject to the lab as we did in the preliminary study, the RA and phlebotomist will travel to the location of each participant. The subject will use the strain in the privacy of their home, and then walk to the mobile lounge lab. The phlebotomist will immediately draw blood and the RA will begin assessments. At the end of the appointment, the subject will be compensated and escorted back to their home.

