**Criteria for inclusion in the study are:**

1. Must be between the ages of 21 and 70 and provide informed consent;
2. Must have prior experience with edibles in order to be eligible to participate in the edible group;
3. Must have used marijuana at least 4x per month in the past month. This includes any form of marijuana consumption including flower, oil, wax, tinctures and edibles;

4. Must not report currently using a strain with greater than 1% CBD or less than 18% THC. This will ensure that there are no subjects who could be harmed by switching to a lower CBD/higher THC strain. All of the subjects in our preliminary study would have met this criterion.
5. Must not be a University of Colorado student or employee;
6. Must report not using other drugs (cocaine, opiates, methamphetamine) in the past 60 days or test positive on a urine test for those drugs of abuse at baseline;
7. Must not smoke greater than 5 cigarettes a day;
8. Must have a breath alcohol level of 0 at screening (to sign consent form) and must not report drinking greater than 3x per week and greater than 5 drinks on occasion for men and 4 drinks on occasion for women;
9. Female subjects must not be pregnant, as indicated by a pregnancy test which will be administered at baseline, or trying to become pregnant;
10. Must not donate plasma, blood, or platelets for 7 days prior to the 2 appointments and 7 days after;
11. Must not be in treatment for psychotic disorder, bipolar disorder or schizophrenia.

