Then they will return to the mobile laboratory for Session 3, where a blood draw self-report measures, and the cognitive battery will be collected in the mobile lab. The blood draw (22 ml), questionnaires and cognitive battery will be repeated at 1 hour after Session 3 at the mobile lab (Session 4). After the last assessment, the participant will be paid \$150 to compensate them for their time and effort (Appointment 1: \$50 for Session 1, Appointment 2: \$50 for Session 2, \$25 for Session 3, \$25 for Session 4), debriefed, and escorted back to their home.

Name of instrument/tool/procedure	Purpose (i.e. what data is being collected?)	Time to Complete
Appointment 1: Baseline/Session 1		
Urine Testing	
 
A urine sample will test for illicit drugs other than marijuana (e.g. cocaine, benzodiazepines, opiates, MDMA, sedatives, or methamphetamine).
 
	
Pregnancy Screening	
 
All female participants will take a urine pregnancy test.
 
	
Demographics Questionnaire	
 
Age, sex, marital status, race/ethnicity, SES, occupation, income, education, and religious affiliation.
 
	
Alcohol Use History Questionnaire	
 
Targets the frequency of lifetime and recent use for alcohol.
 
	
Pain Intensity	
 
Consists of one item asking about the participant's level of pain in the past seven days. Participants are asked to rate their pain on a scale from 0 (no pain) to 10 (worst imaginable pain).
 
	
Promis Pain Interference CAT	
 
This asks participants about how their experience of pain interfered with or affected their enjoyment of various daily activities in the past seven days. The scale is computer-adapted and has a minimum of four questions and a maximum of 12 questions. The questions ask for a response on a 5-point scale. Some of the items are rated: Not at all; A little bit; Somewhat; Quite a bit; Very much; other items are rated: Never; Rarely; Sometimes; Often; Always.
 
	
Health Related Quality of Life	
 
This is a Short Form 36 Health Survey, which consists of 36 questions across nine health domains and is sensitive in detecting changes over time in health-related quality of life.
 
	

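### Edible users share a post-use sampling schedule and a predicted Time 3 to Time 4 fall that suit smoking; their blood THC would usually be rising, so small Time 3 differences could be misread as titration

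*Protocol*

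**What the plan says.** Edible users belong to Study 1. The Overview says "regular edible marijuana users who typically purchase 10 mg products will be allowed to use as they normally would", forming naturally occurring low, medium and high groups. The inclusion criteria name the group: "Must have prior experience with edibles in order to be eligible to participate in the edible group".

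The post-use schedule does not vary by route. Participants use at home and walk to the van, where "The phlebotomist will immediately draw blood and the RA will begin assessments" (Marijuana Administration at Home). The timetable in XII. Procedures shows no wait before Session 3; its hour of relaxation is listed within Session 3.

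Session 4 is defined twice. The Overview puts it "60 minutes after their last use at home". XII. Procedures says the measurements "will be repeated at 1 hour after Session 3 at the mobile lab (Session 4").

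The Hypothesis 1 analysis text expects that "while all groups will decrease in THC over the course of the laboratory appointment between Time 3 and 4", the ordering by THC strain will persist. The Hypothesis 1 factors are strain and time. The Hypothesis 2 predictors are group (or blood THC), time and their interaction. If few reliable group differences appear because participants titrate, Hypothesis 2 switches to blood THC as the exposure and "we will utilize timepoints 3-4 as the within-subjects effect of time".

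**The concern.** Sampling at once and again an hour later, with a fall in between, fits an inhaled product. A swallowed product must first be absorbed, so an early draw can land on the rising part of the curve. That slower course is general pharmacology and is taken here as an assumption, since the protocol does not discuss it.

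Three things are at stake.

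- **Titration.** The plan attributes small group differences in blood THC to self-titration. Among edible users, a small difference at Time 3 may only mean that the product is not yet absorbed. The titration reading also decides which Hypothesis 2 model is run.
- **Exposure.** The rationale for the administration procedure relies on blood level as an objective gauge of dose, however the product is used. A draw soon after swallowing does not support that for edibles. The fallback uses only Times 3 and 4, and the DEQ is collected only at those sessions, so half of the fallback's edible records are affected.
- **Time trend.** If the routes are modelled together, a falling and a rising course are averaged between Times 3 and 4.

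**Working it through.** The plan has no oral timing figure to reproduce. Its sample size (99, or 33 per group) is not in question here.

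**Inputs from the protocol.** Session 3 is drawn on arrival at the van. Session 4 is 60 minutes after last use, or 1 hour after Session 3. The only delay mentioned is the "variable (10 - 20 minute) delay between the time the individual uses the marijuana and the time we can collect the first blood sample", which describes the earlier transport arrangement that the van is meant to improve on.

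**Assumptions, not in the protocol.** One-compartment model with first-order absorption; elimination ke = 0.35/h; time to peak T = 1, 1.5, 2 or 3 h, counted from swallowing and including the lag; lag L = 0, 0.25 or 0.5 h; Session 3 at 10 or 20 minutes after use.

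**Formulas.** The absorption rate ka solves ln(ka/ke)/(ka - ke) = T - L. With u = t - L (zero before the lag ends) and u* = T - L, the level as a fraction of peak is

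F(t) = [exp(-ke·u) - exp(-ka·u)] / [exp(-ke·u*) - exp(-ka·u*)].

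**Worked case, T = 2 h, L = 0.** ka = 0.688/h.

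- At peak: exp(-0.70) - exp(-1.376) = 0.497 - 0.253 = 0.244.
- At 10 minutes: exp(-0.0583) - exp(-0.1147) = 0.943 - 0.892 = 0.052, which before rounding gives F = 21%.
- At 60 minutes: exp(-0.35) - exp(-0.688) = 0.705 - 0.503 = 0.202, so F = 83%.

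**Percentage of edible peak at each time after swallowing.** Values for the 0.25 h lag lie between the two rows shown for each T, or equal one of them.

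| T (h) | L (h) | 10 min | 20 min | 60 min | 70 min |
|---|---|---|---|---|---|
| 1 | 0 | 42 | 69 | 100 | 99 |
| 1 | 0.5 | 0 | 0 | 100 | 98 |
| 1.5 | 0 | 28 | 50 | 94 | 97 |
| 1.5 | 0.5 | 0 | 0 | 85 | 94 |
| 2 | 0 | 21 | 39 | 83 | 89 |
| 2 | 0.5 | 0 | 0 | 66 | 79 |
| 3 | 0 | 14 | 27 | 65 | 72 |
| 3 | 0.5 | 0 | 0 | 45 | 56 |

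**Results over all 12 combinations.**

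- Session 3 is at 0-42% of peak if drawn at 10 minutes, and 0-69% at 20 minutes.
- Session 4 is at 45-100% of peak at 60 minutes after use. At one hour after a 10-minute Session 3 (70 minutes) it is at 56-99%, and about 79% or more in 9 of the 12.
- The level rises from Session 3 to Session 4 in all 12, under either Session 4 definition and for either delay.

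**Sensitivity.** A wider set without lag (time to peak 1-4 h, half-life 1.5-6 h, delay up to 30 minutes) also gives a rise throughout. A fall appears only with a peak near 0.5 h, no lag, and a delay of 15-30 minutes.

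**Dose differences.** In this linear model the level is proportional to dose at every time. A 10 mg product gives 10/2.5 = 4 times the level of a 2.5 mg product at Session 3, as at peak. The absolute difference shrinks by F: in the worked case it is 21% of its peak value at 10 minutes and 83% at 60 minutes. It is zero only when the lag exceeds the delay.

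**The case against.** Much of the opposing case is sound.

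- **The kinetics come from outside.** The protocol gives none, and it does not fix the time from use to Session 3. The immediate draw runs from arrival at the van, so an edible user could stay home longer. This stands and limits the size of the claim. But nothing in the protocol tells edible users to wait.
- **The predicted fall is an expectation, not a decision rule.** The test is an omnibus strain by time interaction over four times, with a quadratic term, and its validity does not need a fall. This stands. The titration reading of small differences does, however, select the Hypothesis 2 model.
- **The sentence may concern flower strains only.** Edible users are not assigned a strain. Against that, Aim 1 covers edibles at low, medium and high THC, and no other course is stated for them.
- **Pooling of routes is not stated.** A statistical analysis plan could separate them. True, but it could not supply later samples that were never drawn.
- **Low THC paired with low effect in the same session still informs an association.** This stands. The fallback is not a false null by construction; what fails is reading the Time 3 level as dose received.
- **Session 4 already reaches most of the edible peak in most cases.** This stands and lowers the severity.

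A reader might infer that Session 3 precedes most absorption, so that edible users show nothing at Time 3 whatever their dose. The documents do not support this. With a 1 h peak and no lag, 1 - exp(-2.178 × 1/3) = 52% of the dose is absorbed by 20 minutes, and proportional dose differences persist once absorption starts.

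**Conclusion.** The point holds as a should-fix. The documents establish one schedule for both routes, a fall predicted for all groups, and no route term in either hypothesis model. Under the assumed range, edible THC is about 0-69% of peak at Session 3 and about 45-100% at Session 4, so it would usually rise. The direction is robust for any time to peak of 1 h or more with a delay up to 30 minutes; the size depends on kinetics and a delay that the protocol does not give.

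The consequence is limited to edible users: attenuated Time 3 differences that could be taken for titration, and a Time 3 blood level that does not represent dose received. How far this affects the overall results depends on the edible share, which the protocol leaves unclear. A reader might also infer that the trial's main comparison fails. It does not: the randomised flower comparison is unaffected if analysed separately.

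**What to change.** - Reconcile the two Session 4 definitions, so that one event starts the clock.
- Record the time of last ingestion for each edible user.
- Either time the edible assessments from ingestion, or keep the sessions and model time since ingestion.
- Analyse edibles separately from flower, or add route and route by time terms.
- Limit the predicted Time 3 to Time 4 decrease to flower users.
- Treat Session 4 as the main post-use point for edibles, and state that a small edible difference at Time 3 is not evidence of titration and does not trigger the Hypothesis 2 fallback. Edible Session 3 data need not be discarded.

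The cost is protocol wording, one recorded time per edible user and a slightly larger model. If edible assessments are timed from ingestion, Appointment 2 may also become longer for those participants. No extra blood samples are needed.

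### The Hypothesis 1 model treats time both as a four-level factor and as a quadratic trend; the quadratic-only reading cannot fit the predicted THC profile and does not match the test that was powered

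*Protocol*

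**What the plan says.** Three parts of Protocol Section IV bear on this.

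- *Power Analysis and Sample Size Requirement.* "The primary analysis is the test of the strain X time interaction effects across repeated assessments of THC in the blood", together with working memory and reward. The calculation is set up as follows: "Using a mixed model ANOVA design, with three groups, four assessment points, and an average ICC = .6 between assessment points", at "two-tailed alpha of .05 and power level of .80". It concludes that "a total n=99 (33 per group) will allow us to detect an interaction effect as small as" f = .12. The study overview likewise describes a mixed factorial design of three strains by four times.
- *Effects of THC Potency on THC Blood Levels, Working Memory, and Reward (Hypothesis 1).* Time is listed as a within-subjects factor with four named levels. "Assuming a significant omnibus test of the interaction, we will decompose the interaction" to find where the strains differ. The model is nevertheless random coefficient regression in Proc Mixed, and the text adds "Note that we will include a quadratic effect in the multilevel model both to appropriately model the quadratic effect" and to see whether that trend differs by condition. No cubic term is named.
- *Hypothesis 2, same section.* It reuses the Hypothesis 1 approach and lists a single time variable and its interaction with group (or blood level) as predictors.

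The predicted course is also in the Hypothesis 1 text. At Time 1 "we do not expect differences in THC since none of the participants will have switched strains". Time 2 is described as sober and before use. A difference is predicted from Time 3 on. All arms then fall to Time 4, with the order high, medium, low kept. No size is given for any gap.

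**The concern.** A quadratic term and random coefficients presuppose numeric time. If time is already a four-level factor, a separate quadratic term adds nothing to it. The text can therefore be read in two ways that give different tests: a strain-by-session interaction on 6 df, or strain-by-linear plus strain-by-quadratic on 4 df.

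The choice matters because of the shape predicted. Two flat points, a jump and a fall is a course with a substantial cubic part. A quadratic smooths it, moving some of the post-use arm difference back to the sober session and lowering the peak. Hypothesis 1 asks at which sessions the strains differ, and that answer would be distorted. The interaction test would also lose the part of the signal the model cannot express.

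**Working it through.** **1. Reproduce the planned power.** Inputs from the power section: N = 99, f = .12, m = 4 assessments, 3 groups, correlation .6, alpha .05. Using the noncentral F for the within-between interaction:

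- lambda = f² × N × m / (1 − rho) = .0144 × 99 × 4 / .4 = 14.256
- df = (3 − 1)(4 − 1) = 6 and (99 − 3)(4 − 1) = 288
- power = .811

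The stated .80 is reproduced, but only with time as a four-level factor.

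**2. Write down the predicted arm gap.** Scale the Time 3 gap to 1. The predictions give (0, 0, 1, r), where r is the Time 4 gap divided by the Time 3 gap. The zero at Time 1 is stated. The zero at Time 2 is implied. The value of r is not given, so it is taken from 0 to 1. All arm differences are assumed to share this time shape.

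**3. Split it into polynomial parts, sessions scored 1 to 4.**

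- linear (−3, −1, 1, 3): (1 + 3r)²/20
- quadratic (1, −1, −1, 1): (r − 1)²/4
- cubic (−1, 3, −3, 1): (r − 3)²/20

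The cubic contrast is r − 3, which is not zero for any r from 0 to 1. At r = 0.5 the parts are .3125, .0625 and .3125, total .6875. The share kept by linear plus quadratic is .375/.6875 = .545.

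**4. Fitted gaps under linear plus quadratic.** Removing the cubic part gives:

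- Time 1: −(3 − r)/20
- Time 2: 3(3 − r)/20
- Time 3: 1 − 3(3 − r)/20
- Time 4: r + (3 − r)/20

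**5. Power on that reading.** Multiply lambda by the share kept and test on 4 and 288 df.

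| r | Fitted gaps, Times 1–4 | Share kept | lambda | Power |
|---|---|---|---|---|
| 0 | −.15, .45, .55, .15 | .40 | 5.70 | .44 |
| 0.25 | −.14, .41, .59, .39 | .44 | 6.23 | .48 |
| 0.5 | −.125, .375, .625, .625 | .545 | 7.78 | .58 |
| 0.8 | −.11, .33, .67, .91 | .71 | 10.1 | .71 |
| 1 | −.10, .30, .70, 1.10 | .80 | 11.40 | .77 |

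The true Time 2 gap is 0 and the true Time 3 gap is 1 in every row.

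**6. Checks.** A simulation with a random intercept and ICC .6 (3,000 runs per setting) at r = 0.5 gave .81 for the factor model and .57 for linear plus quadratic. If the rise shared by all arms is also forced onto a quadratic, the residual is inflated. Power then fell to .52, .39 and .11 for an assumed average rise of 0.5, 1 and 2 SD. Coding time as elapsed days does not remove the misfit: with assumed times 0, 5, 5.06 and 5.10 days and r = 0.5, the fitted gaps are 0, .19, .54 and .78.

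**The case against.** The strongest reply is that the protocol never says linear and quadratic terms replace the factor. The factorial design, the four named levels, the omnibus test, the time-point contrasts and the power calculation all point to categorical time. On that reading the quadratic is one contrast inside the 3-df time effect, and there is no bias and no loss of power. This stands, so the calculated harm is conditional. A second reply is that time coding is normally left to the analysis plan. That carries less weight here, because the protocol itself adds the quadratic and gives its purpose.

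A reader might infer several stronger things that the documents do not support:

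- *That the trial will be biased and have power .58.* This needs the polynomial reading, and the figure also needs r = 0.5, equally spaced sessions and an unchanged total f.
- *That the decline after Session 3 is always hidden.* The fitted gap falls from Time 3 to Time 4 when r is below 0.5, is flat at 0.5 and rises only above it.
- *That any Time 2 gap is an artefact.* Participants have then used the assigned strain for five days, and a zero gap is implied rather than stated.
- *That a single-df contrast, linear in potency, on the post-use minus pre-use mean should replace the omnibus test.* Its power is .93 at r = 0.5 with equally spaced arms. It is .58 at r = 0, and .47 there if only the high arm differs. Gating contrasts behind an omnibus test is a conventional choice, not an error.

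**Conclusion.** The Hypothesis 1 text contradicts itself on how time enters the model, and one of its two readings is unsuitable for the course it predicts. The sample size was justified on the other reading, the 6-df interaction, with power .81.

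If linear and quadratic terms alone are fitted, the sober session shows a false gap of 45% to 30% of the peak. The Time 3 gap is understated by 45% to 30%, and power is about .44 to .77. The misfit holds for every r from 0 to 1. These sizes assume equally spaced session scores, no true gap at Time 2, a time shape common to all arm differences, and f = .12 as planned. The power figures also assume a residual not inflated by misfit of the common time course; otherwise power would be lower. If session is categorical, none of this arises. The ambiguity is thus established, while the harm depends on how it is resolved.

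**What to change.** State in the Hypothesis 1 analysis that session is a four-level categorical factor in Proc Mixed and that the primary test is strain by session on 6 df, as in the power section. Pre-specify the arm contrasts at Times 3 and 4. Delete the quadratic term, or label it a secondary descriptive contrast that does not replace the session factor. Use the same coding for working memory wherever all four sessions are analysed. The fallback for Hypothesis 2 uses only Times 3 and 4, where the question of a quadratic does not arise.

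The cost is about two sentences of text. No extra participants or assessments are needed, and the existing power calculation then applies as written.
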